### Implementation Outcomes

#### 4.1.3 Secondary Outcomes: HCW Feasibility and Acceptability

Feasibility is defined as the extent to which a HCW could engage with the PRC given their available resources such as time, money, and family or job responsibilities. Acceptability is defined as the extent to which HCWs found the tested PRC model satisfying and agreeable.

Quantitative Assessment: At their follow-up assessments (3MFU, 6MFU), HCWs will be given the Feasibility and Acceptability subscales (two separate scales) of a Dissemination &

Implementation measure based on the Consolidated Framework for Implementation Research (CFIR). The measure will be adapted specifically to assessing the implementation of the PRC model for HCWs. We have used this subscale in previous studies in South Africa (for instance in Khayelitsha). Items on this measure will be averaged for an overall feasibility rating from 0 to 3, with higher scores indicating higher feasibility. The primary Feasibility and Acceptability timepoint for HCWs is their 6MFU.

**Qualitative Assessment:** Brief semi-structured interviews assessing perceived feasibility and acceptability of the PRC model will be conducted with HCWs in the Siyakhana condition after their 6MFUs.

#### **4.1.4 Other Outcomes: Patient Feasibility & Acceptability**

Feasibility is defined as the extent to which a patient could engage with the PRC (including in PRC sessions) given their available resources such as time, money, and family or job responsibilities. Acceptability is defined as the extent to which patients found the tested PRC model satisfying and agreeable.

**Quantitative Assessment:** At their follow-up assessments (3MFU, 6MFU), patients will be given the Feasibility and Acceptability subscales (two separate scales) of a Dissemination & Implementation measure based on the Consolidated Framework for Implementation Research (CFIR). The measure will be adapted specifically to assessing the implementation of the PRC model for patients. We have used this subscale in previous studies in South Africa (for instance in Khayelitsha). Items on this measure will be averaged for an overall feasibility rating from 0 to 3, with higher scores indicating higher feasibility. The primary Feasibility and Acceptability timepoint for patients is their 3MFU.

**Qualitative Assessment:** Brief semi-structured interviews assessing perceived feasibility and acceptability of the PRC model will be conducted with patients in the Siyakhana condition after their 6MFUs. These interviews will be combined with interviews on stigma (conducted for R36DA057167).

## 5. ETHICAL CONSIDERATIONS

### Potential Risks to Participants

There is minimal risk from the research procedures in the present study. However, the following risks are still possible:

#### 5.1.1 **Breach to confidentiality**

As with any study, breach of confidentiality is a potential risk. Ways to minimize this risk are described below.

#### 5.1.2 **Psychological or mental discomfort**

It is possible that participants will feel uncomfortable discussing certain topics in trainings, assessments, or PRC sessions. For instance, HCW participants may feel nervous discussing their judgments towards SU, patient participants may feel uncomfortable discussing sensitive topics related to SU and stigma with the peer or study staff, and peers may feel uncomfortable discussing these topics in their training.

#### 5.1.3 **COVID-19 transmission**

Due to the current COVID-19 pandemic, there is a potential risk for COVID-19 transmission between project staff and participants. Efforts to minimize these risks are described below.

### Protections Against Risks

Every effort will be made to minimize all study-related risks. These efforts include:

#### 5.1.4 **Informed consent**

All participants will complete informed consent procedures. To join the study, participants must fully understand and sign the consent form (or, if over the phone, give verbal informed consent after going through the form with the study team member). All participants will have as much time as they want to review the consent form and ask questions. A study team member will also review the form with each participant. The consent form will include all study procedures, information about potential risks and benefits of participation, and information regarding whom they can contact for further questions. It will also state that participation is voluntary, that participants can refuse to answer any question, that participants can withdraw from the study at any time, and that participation (or lack thereof) is in no way related to their employment or care. All procedures and protocols will be approved by the South African Medical Research Council's (SAMRC) Human Research Ethics Committee (HREC) before study initiation.

*Ensuring capacity to provide consent if a person uses substances.* Ensuring that people are not intoxicated at the time of providing consent is important. If a potential participant appears acutely intoxicated, that person will not be consented into the study. The study team will be trained by Drs [name] and [name] on how to detect simple signs of intoxication, such as impaired or slurred speech, smelling of alcohol, impaired co-ordination or balance- if any of these signs are present, we will not enrol a participant or continue with any research activities at subsequent appointments with those already enrolled in the study. To increase our confidence in potential participant's capacity to consent, we include a simple assessment of intoxication in our screening form and assess capacity to provide consent in our consent form, that has been used in other studies with populations of patients who use alcohol.

#### 5.1.5 **Preventing breaches to confidentiality**

The confidentiality of each participant will be respected and maintained. Participant confidentiality will be ensured at all stages of the study.

All data will be kept confidential and only accessible to study staff. Participants' data will be identified by a study identification (ID) number only and a link between the names and ID numbers will be kept separately on a secure server and in a password protected document. This link will be destroyed after the study, including data analysis, has ended. The only individuals who have access to the link are the trained study coordinators on this project in South Africa. The study team at UMD will only have access to data identified with participant ID. Participant documents which include personal identifiers (such as signed consent forms) will be kept in locked files at SAMRC with restricted access. All other de-identified study documents will be kept in a secure location (such as UMD Box) and only study team members will have access to this location.

As part of the informed consent process, all participants will be advised that they may decline to answer any study questions. All study personnel working on the project will receive training about strictly adhering to study protocols regarding participant confidentiality.

Qualitative interviews and sessions will be audio-recorded for analysis. The purpose of the recording will be explained to all participants and informed consent and authorization for recording will be obtained. Digital audio recordings will be uploaded to the study computer immediately following session and the file will be deleted from the recorder/ recording program. Computer files will be secured by a password and will only be accessible to authorized study personnel. The digital recording will be uploaded and stored using a secure project drive (i.e., UMD Box). Following the South African good clinical practice (GCP) guidelines and guidelines set by the American Psychological Association (APA; APA Record Keeping Guidelines, Guideline #7), recordings will be maintained until seven years after the publication of the study. The ethics committee will review study procedures at least annually to review procedures pertaining to participant confidentiality.

### **5.1.6 Protections against psychological or mental discomfort**

All study staff conducting trainings and assessments will be trained to recognize signs of discomfort, distress, or anxiety. Participants will take breaks when necessary to help alleviate any discomfort. Participants will also be reminded that they can refuse to answer any question that makes them uncomfortable and may take breaks whenever they are needed. They will also be informed that they have the right to decline participation in the study, or to withdraw consent at any time without adverse consequences. All patient participants will also be given referrals to local SUD services. HCW participants will be given information about SUD referrals. If needed, mental health referrals will also be given. We have a network of referral resources in the area, established through previous studies in this area.

The PRC(s) will also be trained in recognizing signs of discomfort, distress, and anxiety in the patients they work with. The PRC(s) will be taught about local referral resources and taught to give patients the referrals when needed.

Additionally, there is a study protocol for managing distressed participants that all study staff will receive training in as well as regular supervision and debriefing. This protocol was developed by [name] and has been used across multiple studies with highly vulnerable populations, including traumatized women who use substances, people living with HIV, depression and problem alcohol use, and adolescents with alcohol and depression. In all her studies, [name] has successfully managed all incident cases of distressed participants and there have been no serious adverse or adverse events related to mental health or substance use harms. For participants who are distressed and at risk of harm, we will actively refer and link them to appropriate resources to help them cope with and deal with their

distress. [name] is a registered clinical psychologist (PS 007 1935) and given the size of this study, will be able to provide active and daily clinical oversight to determine the level of care needed for each distressed participant. Our strategies to actively link distressed participants to care include debriefing with the participant. Our study team includes registered psychological counsellors who are trained and have the correct competencies to do this. Strategies will include making (and fast-tracking appointments) at the appropriate agency and accompanying the distressed participant to the agency for their appointment to ensure that they receive the recommended services. [name] has worked in the target communities for more than 15 years and has an established network of mental health and substance use providers to whom we can refer participants should the need arise.

#### **5.1.7 Health and safety: COVID-19**

To reduce the likelihood of COVID-19 transmission, all staff members will be trained in COVID-19 safety protocols and the SAMRC standard operating procedures for the conduct of research during COVID-19. Staff members will have access to personal protective equipment (PPE) which will include masks. All staff members will wear PPE when required by the SAMRC, and can choose to wear PPE when it is not required by the SAMRC. When required by the SAMRC, social distancing (of 1.5m) between staff member and the participant will be practiced, and all surfaces used will be disinfected before and after any trainings/assessments are held. On a case-by-case basis (to be discussed with study managers and PIs), patients and PRCs may choose to have a session over a phone call rather than in-person.

### **Potential Benefits of Proposed Research to Human Subjects and Others**

#### **5.1.8 COPC HCW Participants**

It is possible that HCW participants will not directly benefit from this study. However, HCWs may find that they benefit from the additional information they learn in the training(s), such as general information on SU, SU in the context of HIV, how to screen for problem SU, and how to refer to publicly-funded SUD treatment programs. HCWs in the Siyakhana condition may also enjoy the opportunity to share their feedback on the tested PRC model.

#### **5.1.9 COPC Patient Participants**

It is possible that patient participants will not directly benefit from this study. However, patients may find the treatment referrals—and their COPC HCWs potential increased knowledge of SU and referrals—helpful. Patient participants in the Siyakhana condition may find working with the PRC helpful in their recovery journey, and helpful in getting connected to services and re-engaged in HIV care. Finally, patient participants may enjoy the opportunity to share their feedback on this new PRC model.

#### **5.1.10 Importance of the knowledge to be gained**

From a broader perspective, the current study will be the first to our knowledge to test a novel, adapted PRC model in a low-resource setting for patients struggling with HIV care engagement. As SU stigma among HCWs and patients represent barriers to HIV care engagement, this project will help in understanding how to conduct outreach to people living with HIV and SUD and struggling with HIV care engagement. Further, since this knowledge is being generated within existing COPC teams managed by the Western Cape Department of Health, it has the potential for sustainability and scale-up. Finally, this research will inform future iterations of this model powered to measure effectiveness.

### **Protection of Personal Information (POPI) Act 4 of 2013**

In the consent form, all participants will consent to: their personal information (data) being collected, processed, shared and stored in accordance with this research protocol as approved by the SAMRC HREC; their anonymised data being shared, processed, and transferred by third parties and between third parties

where relevant beyond the jurisdictional borders of South Africa (i.e., to the research team in the United States); and to the findings and results flowing from their anonymised data being broadly shared and published on the conclusion of the research.

In line with the South African POPI act, all data will only be shared securely as outlined in this research protocol. Researchers involved with this project at the University of Maryland in the United States will only have access to de-identified, anonymised data.

## 6. DATA MANAGEMENT

### Data Storage

#### 6.1.1 Data acquisition and transmission

Data collection occurs only in SA at the specified data collection sites. All quantitative data will be entered into an electronic REDCap database (described below). All participants will be given a study ID. Personal identifying information of study participants will be kept entirely separate from their coded data.

Data Integrity. All trainings and assessments will be facilitated by a trained member of the study staff who will be supervised throughout the study. The PRC(s) will also be trained before interacting with patients and will receive regular supervision from trained members of the study team.

Recordings. Qualitative interviews and sessions will be audio recorded for data analysis. The purpose of recordings will be explained, confidentiality will be respected, and informed consent, including the authorization for recording, will be obtained. All recordings will be uploaded to the secure study drive immediately after the interview is complete. Computer recordings will be secured by password and will be accessed only by authorized study personnel. Digital recordings will be stored and moved between sites using a secure, password-protected storage site, such as Box through UMD. In line with the guidelines of the American Psychological Association (APA; APA Record Keeping Guidelines, Guideline #7), recordings will be maintained until seven years after the publication of the study.

Identifiable Data. Consent forms and any other documents with identifiable information will be kept in a separate, secure filing cabinet at the secure SAMRC study site.

De-Identified Data. De-identified data will be kept in a secure electronic system, such as Box through UMD. Only authorized study staff will have access to this data.

Link. The link between the names and ID numbers of participants will be kept separate from all other data on a secure server at SAMRC and in a password protected document. The link will be destroyed after data analysis for the study has ended. Only trained study staff in South Africa will have access to this link.

#### 6.1.2 Data entry methods

##### Qualitative.

*Interviews.* Qualitative data will be collected from in-depth interviews which will be recorded and transcribed. Transcripts will be transferred into MS Word files before being uploaded to NVivo for analysis.

*Sessions.* PRC sessions will be recorded for ongoing supervision purposes.

##### Quantitative Assessments.

Data entry will occur as close to real time as possible to facilitate data management and monitoring of study operations. If assessments are done on paper, they will be scanned by a research assistant as soon as possible and sent to the study's secure server. The paper assessment will then be filed away at a secure location at the MRC and the scanned assessment will be entered on REDCap.

*REDCap.* Demographic and measure data will utilize REDCap through UMD, a secure software toolset and workflow methodology for electronic collection and management of research and clinical trial data in real-time. SAMRC also uses REDCap for data collection. REDCap provides a web-based application with an intuitive interface for users to enter data and have real time validation rules (with automated data type and range checks) at the time of entry. REDCap data collection projects data on a thorough study-specific data dictionary defined in an iterative self-documenting process by all members

of the research team with planning assistance from UMD. All information entered on REDCap will be de-identified in order to protect participants' identities.

#### **6.1.3 Quality assurance**

Data Completeness. To ensure the usability of self-report data, a member of the research team will review all self-report measures to ensure their completeness. Using an electronic data capture system such as REDCap is meant to reduce errors in the data entry and management process. Using REDCap, missing data can be reduced by making items required to answer before moving on to the next item and effort and error associated with data entry can be reduced because there is no manual entering of data at a later timepoint by research assistants.

Confidentiality. Participant data on study materials (including electronic study materials saved on a secure study drive such as Box) will be identified only by participant number and date of visit. By recording the study data in this manner, the information can be considered 'de-identified.'

### **Data safety and monitoring plan**

#### **6.1.4 Regulatory issues**

The procedures laid out in this document will be followed, in compliance with US National Institutes of Health (NIH) requirements as well as South African good clinical practice guidelines, to ensure the safety of study participants and the validity and integrity of data.

Before initiation of this study, the protocol, informed consent, and all other materials used with participants in this study will be reviewed and approved by SAMRC ethics committee. The study team will additionally submit a report to SAMRC ethics committee on an annual basis.

#### **6.1.5 Amendments**

Any changes to the protocol or amendments will be submitted to SAMRC ethics committee before they are implemented.

#### **6.1.6 Reporting definitions**

Unanticipated problems are any incidents/ experiences/ outcomes that are (1) unexpected (in terms of nature, severity, or frequency), (2) related or possibly related to participation in the research, AND (3) suggest that the research places subjects or others at a greater risk of harm (including physical, psychological, economic, or social harm) than was previously recognized.

Adverse events (AEs) are any untoward or unfavourable medical occurrences in a human subject, including any abnormal sign, symptom, or disease, temporally associated with the subject's participation in the research, whether or not considered related to the subject's participation in the research.

Serious adverse events (SAEs) are any adverse events that meet any of the following criteria: (1) results in death; (2) is life-threatening; (3) requires inpatient hospitalization or prolongation of existing hospitalization; (4) results in a persistent or significant disability/ incapacity; (5) results in a congenital anomaly/ birth defect; OR (6) may jeopardize the subject's health and may require medical or surgical intervention to prevent one of the other outcomes listed in this definition.

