**ETAU Patients.** Patients seen by the ETAU COPC will continue to receive normal treatment from their COPC HCWs (i.e., normal efforts to re-engage patients in HIV care). These normal visits will be enhanced through (1) their COPC HCWs knowing how to, and therefore, potentially screening them for problem SU, and (2) their COPC HCWs knowing how to give referrals to local SU treatment programs. It is also possible that they will receive enhanced care from their COPC HCWs due to their COPC HCWs now knowing more about SU in the context of HIV.

**Siyakhana (PRC+ETAU) Patients.** Patients seen by the Siyakhana COPC will be invited to attend sessions with a PRC after their baseline assessment.

The structure and content of PRC sessions were designed based on patient and stakeholder feedback about PRCs (Protocol IDs: EC049-11/2021, EC046-10/2020). Siyakhana patient participants will be invited to meet with the PRC on a regular basis for approximately 12-weeks (3-months). Each meeting will be scheduled to last approximately 30 minutes, although an hour will be allocated for each meeting. The PRC and patient together will decide where to meet in a venue that is physically and psychologically safe for both the PRC and patient. Options deemed safe by stakeholders and patient participants in our formative work included the library, the local clinic, community centers, and for some, their homes. The location that the PRC and patient chooses will be recorded so that we have this information for future iterations of this project. The goal of these meetings will be for the PRC to motivate the patient to return to HIV care and seek SUD treatment. In training the PRC, the PRC will have attained competence in providing brief education around SU and HIV, supporting the patient in their recovery, and helping the patient problem-solve barriers to accessing both HIV and SU care.

Figure 2. Patient Procedures

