#### **6.1.8 Adverse events and unanticipated problems**

As this study consists of low-risk meetings with a PRC, we do not anticipate having any study-related AEs, SAEs, or unanticipated problems. However, given that many participants in this study are from a vulnerable population (i.e., PLWH and SUD who have fallen out of HIV care), and are enrolled for about six-months, it is possible that AEs, SAEs, and unanticipated problems will arise. The plan for monitoring and reporting AEs, SAEs, and unanticipated problems is below.

**Monitoring.** At follow-up assessments, study staff will ask participants if they experienced any AEs or SAEs since the last assessment (e.g., hospitalizations). The PRC(s) will also be trained to let the study team know if they are aware of any AEs or SAEs.

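### Breach of confidentiality is a named risk, but no follow-up question asks about non-medical harm and the promised reporting plan for unanticipated problems is missing

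*Combined protocol and SAP*

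**What the plan says.** Section 5 lists three possible risks, and the first is confidentiality: "As with any study, breach of confidentiality is a potential risk" (5.1.1). Section 5.1.5 describes how breaches are to be prevented; it does not say how one would be detected.

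Section 6.1.6 defines AEs as "any untoward or unfavourable medical occurrences in a human subject", and SAEs are a subset of AEs. It also defines unanticipated problems more broadly. These must be "unexpected (in terms of nature, severity, or frequency"), must be at least possibly related to the research, and must suggest a "greater risk of harm (including physical, psychological, economic, or social harm) than was previously recognized". All three criteria have to be met.

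Section 6.1.8 says that a plan for AEs, SAEs and unanticipated problems follows. The monitoring text then reads: "study staff will ask participants if they experienced any AEs or SAEs since the last assessment (e.g., hospitalizations"). For the coach: "The PRC(s) will also be trained to let the study team know if they are aware of any AEs or SAEs". The ethics committee rules that follow cover AEs (yearly report) and SAEs (within 48 hours). There is no corresponding line for unanticipated problems.

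Under 6.1.7, protocol violations that staff become aware of go to the PIs and then to the ethics committee within 7 days. The statistical analysis plan (section 4) contains no tabulation of harms by arm.

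**The concern.** In a trial about stigma, having one's HIV or substance-use status become known through study contact is a foreseeable harm. It bears on whether the model is acceptable and worth scaling up. It is not in itself a medical occurrence, so a participant asked only about AEs and SAEs, with hospitalization as the example, has no prompt to mention it.

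The arms also differ in contact. Only Siyakhana patients are invited to PRC sessions, at places that "included the library, the local clinic, community centers, and for some, their homes" (COPC Patients: Procedures). Those sessions are recorded (6.1.2), and only Siyakhana patients have an exit interview. If these events surface only by chance, both the exposure and the opportunity to detect it can differ by arm. A blank record could then be read as support for the low-risk description in 6.1.8 when it mainly reflects that nobody asked.

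**Working it through.** The plan states no figure on this point, so there is none to reproduce. The check has two parts.

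**1. Following an ordinary breach through the plan's own routes**

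- *AE or SAE (6.1.6):* not met by the disclosure itself, which is not a medical occurrence. A resulting symptom could qualify.
- *Unanticipated problem (6.1.6):* social harm is within scope. A breach is already listed in 5.1.1, so it may not be unexpected in nature. It could still be unexpected in severity or frequency, but frequency cannot be judged unless someone asks. If the event did qualify, 6.1.8 gives no procedure for finding or reporting it.
- *Protocol violation (6.1.7):* works if study staff broke the protocol and staff become aware of it. It does not clearly cover a patient being recognised while meeting the PRC.
- *PRC report (6.1.8):* limited to AEs and SAEs, and available only where there is a PRC.
- *Exit interview (after 6MFU):* Siyakhana only, and breach is not a listed domain.

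No route asks patients in both arms about non-medical harm.

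**2. How informative a blank record would be (illustration)**

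Inputs from the documents: 25 patients per arm (COPC Patient: Eligibility), and up to 20% attrition or missing records in the enrolment rationale, giving 25 × 0.80 = 20. Assumptions: true risk p of 5–10%, and a share s of events that reaches staff.

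P(at least one event recorded) = 1 − (1 − p·s)^n

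With every patient asked and reporting (s = 1):

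- n = 25: 1 − 0.95^25 = 0.72; 1 − 0.90^25 = 0.93
- n = 20: 1 − 0.95^20 = 0.64; 1 − 0.90^20 = 0.88

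With passive capture only, n = 25:

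| Share reaching staff | p = 5% | p = 10% |
|---|---|---|
| 10% | 0.12 | 0.22 |
| 25% | 0.27 | 0.47 |
| 50% | 0.47 | 0.72 |

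Upper one-sided 95% bound if all are asked and none report, 1 − 0.05^(1/n): 11.3% for n = 25 and 13.9% for n = 20.

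For contact, the session guideline gives 1 + 3 + 2 = 6 PRC meetings before the final as-needed month, nominally 6 × 25 = 150 in Siyakhana and none in ETAU. The protocol calls this schedule a guideline and allows sessions to be added or removed, so 150 is indicative and not a minimum.

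**The case against.** A reader might infer that a breach can never be counted and that the safety record must show none however often it happens. The documents do not support that. Unanticipated problems include social harm and can be triggered by unexpected severity or frequency. Staff breaches have a 7-day route under 6.1.7. Psychological effects of a disclosure could be AEs.

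There are other safeguards too. Patient and PRC choose together a venue safe for both, and its location is recorded. The PRC is supervised weekly or biweekly. Section 5.1.6 describes a distress protocol with daily clinical oversight. Stigma is self-reported at both follow-ups in both arms.

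It is also fair to say that 5.1.1 and 5.1.5 are mainly about data handling, much of which applies to both arms. Being seen with the PRC is not named there and might count as unexpected in nature. Unwanted disclosure is my term, and unequal exposure is an inference from the procedures that the protocol does not state.

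All of this stands, and it limits the point. It does not remove it. None of these routes is described as a fixed question on breach or disclosure (the assessment forms are not in the documents), and several exist only in Siyakhana. An event that does qualify as an unanticipated problem still meets a section that promises a procedure and does not give one.

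**Conclusion.** The point holds as a gap in ascertainment and reporting. The definition of AEs is not in itself an error. Non-medical harm has a definition in 6.1.6 but no active question, no written monitoring or reporting procedure, and no planned count by arm. What is captured would be captured passively, with opportunities that differ by arm, so the counts could not be compared fairly and a blank record would be weak evidence of low risk.

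The size depends on assumed rates. At a true risk of 5–10% at least one event is more likely than not in an arm of 20 to 25, yet if only a tenth of events reached staff the chance of recording any among 25 would be 12–22%. Asking does not make a pilot of this size precise: zero reports would still be compatible with a rate of about 11–14%.

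The primary stigma outcome and the power statement for patient re-engagement are unaffected. In a minimal-risk pilot this is an inexpensive improvement that should be made, together with repair of the omission in 6.1.8.

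**What to change.** In 6.1.8:

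- Add one fixed question to the patient 3MFU and 6MFU in both arms. It should cover breach of confidentiality, unwanted disclosure of HIV or substance-use status, or other social harm linked to study contact, recorded whether or not the event was expected.
- Extend the PRC's reporting duty to these events.
- Supply the monitoring and reporting text for unanticipated problems that the section announces.

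In section 4, tabulate these events by arm with the AEs, giving the number of patients asked as the denominator.

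The cost is about one minute per assessment at two existing contacts, a short addition to PRC training, and one table row. No new visit or change in sample size is needed.
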